## 5.6 CENTRAL PATHOLOGICAL REVIEW

Central pathological review will be conducted by experienced pathologists appointed by the Sponsor and available to the investigative sites for consultation about AITL diagnosis confirmation. Central pathological review is required for (a) local histopathology reports prior to patient treatment, and (b) tumor samples before each futility analysis and at the end of the study: see also [Figure 3. Study design](#).

The central laboratory pathologists will be responsible for (a) approving patient inclusion on the basis of investigative site pathology reports provided during screening, (b) analyzing tumor biopsies (initial diagnosis and/or relapses) to confirm the AITL diagnosis, and (c) analyzing blood samples to identify plasma biomarkers and extract DNA.

Tumor samples (initial diagnosis and relapses) are required for central review to confirm AITL diagnosis but not to approve inclusion. Archived tissue samples of representative tumors must be sent for central review and biomarker analysis. If the diagnosis biopsy is not available (because the patient was diagnosed at another site, for example), the most recent representative biopsy (relapse and/or progression) will be used. Submitting both, however, is strongly recommended. Tumor blocks will be returned to the centers.

Samples requirements are as follows:

- Archived tissue samples of representative tumors:
  - A formalin-fixed paraffin-embedded (FFPE) tissue block (preferred), usually from lymph node excisional biopsy.

or

- Freshly-cut unstained tumor slides.
- One whole blood sample for germline DNA extraction (6 mL) and another blood sample (4 mL) to obtain plasma are required for biomarker analyses: 10 mL will be collected in EDTA tubes will be collected at the same time as the first PK sample (prior to infusion) on Day 1 of Cycle 1.

Central pathological confirmation of AITL diagnosis for the 15 and 30 patients in the futility analyses is mandatory and for all patients at the end of the study; the central review pathologists will also be available when required for consultation in controversial cases and at the investigators' discretion.

Tissue sample specifications (number and thickness) must be confirmed in advance with the central laboratory. Procedures for collection, handling, and shipping of the samples will be provided in a separate instruction manual for sites.

## 5.7 PATIENT RANDOMIZATION

Not applicable.

## 5.8 EVALUATIONS DURING TREATMENT

The assessments listed in [Table 5](#) below will be made while the patient is on treatment: see also [Figure 3. Study design](#).

**Table 5.** Evaluations during treatment.

	ASSESSMENT	TIME
1. Clinical examination	
 
◆ Complete physical examination, including weight and BSA.
 
◆ Basic neurological examination.
 
◆ Performance status (ECOG PS).
 
◆ Vital signs: heart rate, blood pressure and body temperature.
 
	By Day 1 of each cycle (always prior to plitidepsin administration).
	
 
◆ Concomitant therapies.
 
	Throughout the on-treatment period.
2. Laboratory tests	
 
◆ Hematology: differential WBC, hemoglobin, hematocrit and platelets.
 
	Cycle 1: Day 1, 8, 15 and 22 (always prior to plitidepsin administration). Not necessary on C1D1 if performed within the seven previous days and there is no change in the patient's clinical status and medications. To be performed at least every other day in the presence of grade 4 non-febrile neutropenia or febrile neutropenia, and every day in the presence of grade 4 thrombocytopenia until recovery. Cycle 2 and beyond: Day 1, 8 and 15 of each cycle (always prior to plitidepsin administration).
	
 
◆ Biochemistry-A: AST, ALT, total bilirubin (direct bilirubin if total bilirubin > 1.5 × ULN), ALP, creatinine, calculated creatinine clearance (Cockcroft-Gault formula), glucose, serum electrolytes (Na+, K+, Mg++, Ca++) and CPK (CPK-MB fraction should be measured if CPK is abnormally high).
 
	Cycle 1: Day 1, 8, 15 and 22 (always prior to plitidepsin administration). Not necessary on C1D1 if performed within the seven previous days and there is no change in the patient's clinical status and medications. To be performed at least every other day in the presence of grade 3/4 vomiting or any other drug-related SAE. Cycle 2 and beyond: Day 1, 8 and 15 of each cycle (always prior to plitidepsin administration).
	
 
◆ Biochemistry-B: Uric acid, LDH, total proteins, albumin and C-reactive protein.
 
	Day 1 of each cycle (always prior to plitidepsin administration). Not necessary on C1D1 if performed within the seven previous days and there is no change in the patient's clinical status and medications.
	
 
◆ Coagulation tests: PT, PTT and INR.
 
	Day 1 of each cycle (always prior to plitidepsin administration).
	
 
◆ Urine elemental dipstick and sediment.
 
	Repeat if clinically indicated.
	
 
◆ Complete serology
 
◆ Coombs test
 
◆ Serum immunoglobulin quantification.
 
◆ Serum protein electrophoresis.
 
	Repeat if clinically indicated.
3. Central pathological review	Tumor tissue sample.	Ship prior to futility analysis (or as instructed).

	ASSESSMENT	TIME
4. Pharmacokinetics	See Table 6 Sampling schedule for the determination of plitidepsin.	Day 1, 8 and 15 of Cycle 1.
5. Biomarker analysis	Tumor tissue sample. Collect 10 mL blood: one whole blood sample for germline DNA extraction (6 mL) and another blood sample (4 mL) to obtain plasma. A separate instruction manual for sites will be provided.	Tumor biopsy obtained at diagnosis or relapse. (See point 3 above.)  Blood draw CID1: with the first PK sample (before plitidepsin infusion).
6. Pregnancy test	Only if the patient is a WOCBP. Assessment of $\beta$ -hCG.	Repeat every cycle (or, at least, every month).
7. Cardiac assessment	♦ ECG: Rhythm, frequency and QT interval should be specifically described, besides any ECG anomaly or variation respect to baseline.	First cycle, Day 1: Prior to the first infusion (unless performed as part of screening within the previous 14 days), at the end of the first infusion, at 30 min post-infusion and at 1-hour post-infusion (see Table 6 ). First cycle, Day 8 and Day 15: Prior to the infusion, and at 1-hour post-infusion (see Table 6 ). Further cycles: prior to each infusion.
	♦ LVEF by ECHO or MUGA.	Repeat if clinically indicated.
8. Bone marrow biopsy/aspirate		Repeat if clinically indicated.
9. Chest X-ray		Repeat if clinically indicated.
10. Tumor assessment	Radiological (PET-CT + CT*) and clinical tumor assessment.  In the case a patient continues in treatment beyond Cycle 6, CT scans may be used every four months (+ 2 weeks) for the first two years and every six months (+ 2 weeks) thereafter, but any subsequent improvement in response should be confirmed by PET-CT*.  Disease progression at any time during the study should be confirmed by imaging (if the physical condition of the patient permits).	One to two weeks after last dose of Cycle 3 and at least 4 weeks (but no more than 8 weeks) after last dose of Cycle 6 (or earlier in the event of treatment discontinuation for whatever reason). Cycle 4 can be started without waiting for the results of the Cycle 3 tumor assessment. No radiological assessment is necessary in the event of discontinuation due to any reason other than PD during or after Cycle 4 if the Cycle 3 radiological assessment has been performed correctly.
11. Concomitant medications	All concomitant therapies taken by the patient (including any not prescribed by the Investigator) should be documented with indication from two weeks prior to starting study treatment.	Throughout the on-treatment period.
12. Adverse events **	As per NCI-CTCAE v.4.	Throughout the on-treatment period.

\* When PET-CT is performed it must be in combination with diagnostic quality CT with intravenous contrast (except medically contraindicated). Two alternatives are allowed: Hybrid PET CT scanners may be used to acquire diagnostic quality CT which includes intravenous contrast OR PET CT without intravenous contrast and diagnostic quality CT images with intravenous contrast using a standalone CT scanner must be performed.

\*\* Clinical assessment of the patient's signs and symptoms (if any and including nurses' assessment and patient-reported issues) should continue on an ongoing basis throughout the study and be reported at least every cycle (unless relevant enough to program an unscheduled visit or the criteria for seriousness are reached and an SAE report is required). Assessments for a particular visit do not need to all take place on the same day but should all be within the planned time window. Physical examination and laboratory assessments, for example, can be performed more frequently during the study if clinically required.

Permitted windows for assessments

±1 day for study treatment administration and clinical assessments (ECOG PS, vital signs, weight, BSA, neurological assessment—always prior to infusion).

-2 days for hematology, biochemistry-A, serum  $\beta$ -2 microglobulin, biochemistry-B and coagulation tests. Note: windows for laboratory assessments only apply prior to the scheduled infusion, that is within 48 hours before the next scheduled infusion (except CID1).

ALT, alanine aminotransferase; ALP, alkaline phosphatase; AST, aspartate aminotransferase; BSA, body surface area; CPK, creatine phosphokinase; CPK-MB, creatine phosphokinase-isoenzyme MB; ECG, electrocardiogram; ECOG, Eastern Cooperative Oncology Group;  $\beta$ -hCG, beta subunit of human chorionic gonadotropin; INR, international normalized ratio; LDH, lactate dehydrogenase; NCI-CTCAE, National Cancer Institute Common Terminology Criteria for Adverse Events; PS, performance

	ASSESSMENT	TIME
--	------------	------

status; PT, prothrombin time; PTT, partial thromboplastin time; SAE, serious adverse event; WBC, white blood cells; WOCBP, woman of childbearing potential.

## 5.9 EVALUATIONS AT END OF CYCLE 6

A PET-CT + CT scan for radiological tumor assessment is required at least four weeks (but no more than 8 weeks) after last dose of Cycle 6 (or earlier in the event of treatment discontinuation for whatever reason; no radiological assessment is necessary in the event of withdrawal due to any reason other than PD during or after Cycle 4 if the Cycle 3 radiological assessment has been performed correctly) or at suspected clinical progression while on treatment.

The End of Cycle 6 visit should take place 4–8 weeks after last dose of Cycle 6 (when the PET-CT results are available). If a patient is shown to have SD or PR at this assessment, treatment can resume (Cycle 7) and evaluations will continue as described in Section 5.8. If a patient is shown to have CR or PD, the patient should be discontinued and the EOT visit performed as soon as possible: see also [Figure 3. Study design](#).

The following assessment should be performed/evaluated:

- Assessment of disease-related symptoms.
- Complete physical examination (including weight and BSA).
- Basic neurological examination.
- ECOG PS.
- Vital signs (heart rate, blood pressure, body temperature).
- Concomitant therapies.
- Hematology.
- Biochemistry-A.
- Tumor assessment (clinical and radiological using PET-CT + CT).
- Adverse events.
- Bone marrow biopsy/aspirate assessment (if involved at diagnosis).

If the patient does not resume treatment in Cycle 7, adverse events must be reported during 30 days after the last study drug administration. All serious adverse events (SAEs) occurring within 30 days of the last study drug administration will be reported. Beyond this period of time, only those suspected to be treatment-related SAEs will be reported (Section 8.6.2).

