### 5.2 PLANNED TRIAL PERIODS (INDIVIDUALLY PER PATIENT)

Patients will be evaluated at scheduled visits in three study periods:

- **Pretreatment:** from signature of the informed consent to the first dose of study treatment.
- **Treatment:** from first dose of study treatment to EOT (see Section [5.2.1.1](#)). EOT is defined as 30 days ( $\pm$  one week) after the day of last administration of study treatment or as soon as possible after End of Cycle 6 radiological and clinical assessments (if the patient discontinues: see [Figure 3](#) below), unless the patient starts a new antitumor therapy or dies within 30 days from the last dose, in which case the date of administration of this new antitumor therapy or the date of death will be considered the EOT date.
- **Follow-up:** after EOT, patients will be followed every four weeks until resolution of all toxicities (if any). Patients who discontinue treatment without progression will be followed every four months (+ two weeks) for the first two years of follow-up, and every six months (+ two weeks) thereafter, unless clinically indicated, until PD, start of other antitumor therapy, death or the date of study termination (clinical cutoff), whichever occurs first. After documented progression or start of a new antitumor therapy, patients will be followed for survival approximately every four months during the first two years, and then approximately every six months until death or the date of study termination, whichever occurs first. For the purpose of collecting information on patient's survival exclusively, a documented telephone call is acceptable; follow-up for survival will be completed for all patients only if results of the primary endpoint confirm the trial as positive.

Patients will be considered to be **on-study** from the signature of the informed consent form (ICF) to the end of the follow-up period (or screening failure). Investigators can appraise potential study candidates in a pre-screening period but only perform study-specific screening assessments after the patient formally consents. Patients will be considered to be **on-treatment** from the date of first dose until EOT.

**Figure 3.** Study design.

Central pathological review involves different analyses in two separate processes: (a) of local histopathology reports before approving patient inclusion, and (b) of tumor samples before each futility analysis and at the end of study.

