## 5.10 EVALUATIONS AT END OF TREATMENT

The *end-of-treatment visit* (EOT) should take place approximately 30 days ( $\pm$  one week) of the last plitidepsin administration or as soon as possible after the End of Cycle 6 radiological and clinical assessments (if the patient discontinues), unless the patient

---

 When PET-CT is performed it must be in combination with diagnostic quality CT with intravenous contrast (except medically contraindicated). Two alternatives are allowed: Hybrid PET CT scanners may be used to acquire diagnostic quality CT which includes intravenous contrast OR PET CT without intravenous contrast and diagnostic quality CT images with intravenous contrast using a standalone CT scanner must be performed.

starts any subsequent antitumor therapy, in which case the EOT visit should be performed immediately before the start of the new therapy (ideally the day before or the same day): see also [Figure 3. Study design](#).

Treated patients, regardless of the reason for ending the treatment, will undergo the following EOT assessments:

- Assessment of disease-related symptoms.
- Complete physical examination (including weight and BSA).
- Basic neurological examination.
- ECOG PS.
- Vital signs (heart rate, blood pressure, body temperature).
- Concomitant therapies.
- Hematology.
- Biochemistry-A.
- Biochemistry-B.
- Pregnancy test.
- Coagulation tests.
- Serum immunoglobulin quantification.
- Serum protein electrophoresis.
- Adverse events.

For individual patients (and if clinically indicated according to Investigator's criteria), it might also include the following:

- Chest X-ray (if needed).
- Bone marrow biopsy/aspirate (if involved at diagnosis).
- Other tests as appropriate.

All these evaluations will only have to be repeated for those parameters for which no measurement is available within ten days before the EOT visit, or for those parameters with values that were out of range in the last assessment (grade  $\geq 2$  according to NCI-CTCAE v.4).

Adverse events must be reported during 30 days after the last study drug administration. All serious adverse events (SAEs) occurring within 30 days of the last study drug administration will be reported. Beyond this period of time, only those suspected to be treatment-related SAEs will be reported (Section [8.6.2](#)).

The Sponsor will evaluate all safety information that is spontaneously reported by an Investigator beyond the time frame specified in the protocol.

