## **8.6 ADVERSE EVENTS REPORTING PROCEDURES**

### **8.6.1 Reporting Adverse Events**

The Sponsor will collect AEs until 30 days after administration of the last dose of study drug(s)/IMP(s) or until the start of a new antitumor therapy, whichever occurs first. All AEs suspected to be related to the study drug/IMP must be followed-up after the time of therapy discontinuation until the event or its sequelae resolve or stabilize at an acceptable level to the Investigator and the Sponsor.

All AEs, including misuse, overdose, abuse and medication error, must be recorded in English using medical terminology in the source document and the e-CRF. Whenever

possible, the Investigator will record the main diagnosis instead of the signs and symptoms normally included in the diagnoses.

Investigators must assess severity (grade) of the event following the NCI-CTCAE v.4 and assign a relationship to each study drug(s)/IMP(s); and pursue and obtain information adequate both to determine the outcome and to assess whether it meets the criteria for classification as a SAE requiring immediate notification to the Sponsor or its designated representative. The Investigator must provide any relevant information as requested by the Sponsor in addition to that on the e-CRF.

Abnormal laboratory tests occurring during the study should only be recorded in the AE section of the e-CRF if the disorder:

- is associated with clinically significant symptoms, and/or
- leads to a change in study dosing or discontinuation from study treatment, significant additional concomitant drug treatment or other therapy, and/or
- leads to any of the outcomes included in the definition of a SAE.

Otherwise, laboratory results should be reported in the corresponding section of the e-CRF (e.g. biochemistry, hematology).

Disease progression or appearance of new tumor lesions, or any sign or symptom clearly related with this circumstance is NOT an AE.

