#### **8.6.2 Reporting Serious Adverse Events**

The Sponsor will collect SAEs from the time of signing of the ICF until 30 days after administration of the last dose of study drug(s)/IMP(s) or until the start of a new antitumor therapy, whichever occurs first (or until screening failure, if applicable). Beyond this period of time, only those SAEs suspected to be related to the IMP will be collected. Nonetheless, the Sponsor will evaluate any safety information that is spontaneously reported by an Investigator beyond the time frame specified in the protocol.

All SAEs (as defined above) that occur after patient registration, regardless of relationship to the study drug(s)/IMP(s) must be reported immediately and always within 24 hours to the PharmaMar Pharmacovigilance Department electronically by completing the applicable e-CRF sections. Only in the event of electronic system failure can SAEs be reported using a paper “SAE form” by fax ([contact]), e-mail ([contact]), or by telephone ([name]). Out of office hours [Greenwich Meridian Time (GMT)], assistance on SAE reporting can be obtained by calling the Pharmacovigilance Department at [contact]. SAEs initially reported by alternative (i.e., not electronic) methods must be followed by a completed electronic SAE reporting on e-CRF from the investigational staff within one working day.

Those SAEs occurring during the screening phase (from ICF signature to registration) and after off-study will be reported using a paper “SAE Form” that must be forwarded as mentioned above always within 24 hours to the Pharmacovigilance Department by fax or e-mail.

All SAEs suspected to be related to the IMP(s) must be followed until the event or its sequelae resolves or stabilizes at an acceptable level by the Investigator and the clinical monitor or his/her designated representative.

Disease progression or appearance of new tumor lesions, or any sign or symptom clearly related with this circumstance should NOT be reported as an SAE.

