8.2 Treatment administration

CRF cycles with a theoretical duration of 4 weeks will be used for this analysis.

Total cumulative dose, time on treatment, dose intensity and relative dose intensity, cycle delay, dose omissions, and dose reductions will be described following standard tables detailed in Appendix I.

Total cumulative dose, expressed in mg/m² is the sum of all the plitidepsin doses from the first cycle until last cycle including the dose received in last cycle.

Patients will be considered to be on-treatment for the duration of their treatment and 30 days following the last treatment dose. If the patient starts any new antitumor therapy outside this clinical trial or dies within 30 days of last treatment dose, the date of administration of this new therapy or the date of death will be considered the date of treatment discontinuation.

However, as a convention, for dose intensity calculation purposes, the duration of the last cycle is considered to be 28 days.

Intended dose intensity is the planned dose per cycle divided by the planned number of weeks by cycle (2.4mg/m²/wk for plitidepsin).

Absolute dose intensity is the actual cumulative dose divided by the number of weeks of treatment. Relative dose intensity (%) is the ratio of absolute dose intensity divided by the intended dose intensity.

The item «Infusion delayed: yes/no» in the case report form (CRF) will be used to calculate the delay (on day 1 infusion). For cycles considered as delayed by the investigator, the delay will be calculated as:

Delay: Date of current drug administration – Date of previous drug administration – 28.

The first infusion of the first cycle will be excluded from all cycle delay and cycle modification calculations.

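### For patients who reach the End of Cycle 6 visit, the protocol sets two different end dates for collecting new AEs and unrelated SAEs, up to 26 days apart by that visit

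*Protocol*

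**What the plan says.** **End date at EOT.** Protocol 5.2 defines the on-treatment period as running "from the date of first dose until EOT". The Schedule of Assessments and Table 5 (Section 5.8) have adverse events recorded for the whole of that period. Adverse events are also a listed assessment at both the End of Cycle 6 visit (5.9) and the EOT visit (5.10).

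**When EOT occurs after Cycle 6.** Section 5.9 states: "The End of Cycle 6 visit should take place 4–8 weeks after last dose of Cycle 6". A patient with SD or PR may then go on to Cycle 7. A patient with CR or PD stops and has the EOT visit as soon as possible. Section 5.2.1.1 acknowledges that this visit shifts EOT away from the usual 30 days.

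**End date at day +30.** Section 5.9 states: "If the patient does not resume treatment in Cycle 7, adverse events must be reported during 30 days after the last study drug administration". For SAEs, 5.9 and 5.10 both say: "All serious adverse events (SAEs) occurring within 30 days of the last study drug administration will be reported". Section 8.2 treats EOT and day 30 as the same point. Sections 8.6.1 and 8.6.2 collect events "until 30 days after administration of the last dose of study drug(s)/IMP(s) or until the start of a new antitumor therapy, whichever occurs first".

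**After day +30.** Section 5.9 adds: "Beyond this period of time, only those suspected to be treatment-related SAEs will be reported". Sections 5.10 and 8.6.2 agree, and none of them gives an end date for related SAEs.

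**SAP.** Section 7.1 admits events to the AE tables from the first infusion onward and sets no upper date. Section 8.2, on exposure, says: "Patients will be considered to be on-treatment for the duration of their treatment and 30 days following the last treatment dose".

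**The concern.** The protocol moves EOT to accommodate the post-Cycle 6 PET-CT, but the reporting rules were not moved with it. Between day +31 and the visit, one set of sections requires new AEs and all SAEs, and another requires only SAEs suspected to be related.

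The cutoff in 5.9 also depends on a fact not yet known. It applies if Cycle 7 does not start, and that is settled only once the PET-CT has been read. Because response largely determines who may resume, capture of unrelated SAEs and new AEs in this interval would depend on efficacy outcome. In a single-arm trial with no control group to show such an imbalance, that is an avoidable weakness in the safety data.

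The tables are affected too. SAP 7.2 maps EOT laboratory values to the last cycle whatever their date. A laboratory abnormality on day +50 is therefore counted, while a clinical AE on the same day appears or not according to which section the site followed.

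**Working it through.** The plan states no figure on this point, so there is none to reproduce. The check is date arithmetic followed by a comparison of the rules.

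**Inputs.** End of Cycle 6 visit 4 to 8 weeks after the last Cycle 6 dose (5.9). Cutoff 30 days after the last dose (5.9, 5.10, 8.2, 8.6.1, 8.6.2). EOT for other patients 30 days ± one week (5.2, 5.10). SAE reporting time 24 hours (8.6.2).

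**Step 1: permitted visit days.** 4 × 7 = 28 and 8 × 7 = 56, so the visit falls on day +28 to +56. That is 56 − 28 + 1 = 29 days. Days +28, +29 and +30 lie inside the cutoff, leaving 29 − 3 = 26 after it (26/29 = 90%). On the nominal schedule the last Cycle 6 dose is on study day 5 × 28 + 15 = 155, the cutoff is day 185, and the visit window is days 183 to 211.

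**Step 2: gap by visit week (visit day − 30).**

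| Visit | Day | Days past cutoff |
|---|---|---|
| 4 weeks | 28 | −2 (no gap) |
| 5 weeks | 35 | 5 |
| 6 weeks | 42 | 12 |
| 7 weeks | 49 | 19 |
| 8 weeks | 56 | 26 |

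Any delay from this visit to EOT comes on top; the protocol gives no number for it.

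**Step 3: patients who stop before the End of Cycle 6 visit.** EOT falls on day 30 − 7 = 23 to 30 + 7 = 37, so it is at most 37 − 30 = 7 days past the cutoff.

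**Step 4: an SAE on day +40, with the visit on day +56.**

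| SAE judged | Cycle 7 starts | Patient stops, 30-day rule | Patient stops, on-treatment-to-EOT rule |
|---|---|---|---|
| Related | Due | Due | Due |
| Unrelated | Due: the last dose is now later | Not due | Within the on-treatment period |

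The resumption decision comes 56 − 40 = 16 days after the event, against a 24-hour reporting time. New AEs follow the same pattern as unrelated SAEs, without the 24-hour clock.

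**Step 5: new antitumor therapy within 30 days.** Sections 5.9 and 5.10 ask for every SAE within 30 days and make no exception. Sections 8.2, 8.6.1 and 8.6.2 stop at the start of the new therapy if that is earlier. An unrelated SAE on day +25 after a switch on day +20 is therefore due under one pair of sections and not under the other three.

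**The case against.** The strongest reply is that this is inconsistent wording and not a demonstrated loss of data. Most of the stronger readings a reader might infer do fail:

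- **SAE collection closes at day 30.** It does not. SAEs suspected to be related remain reportable with no end date, related AEs are followed until they resolve or stabilize (5.11, 8.6.1), and the sponsor evaluates spontaneous late reports (5.10, 8.6.2).
- **Events are lost.** That is only one of two readings. Under 5.2 with Table 5, AEs are collected to EOT, and SAP 7.1 would tabulate them.
- **Patients who resume are unmonitored between Cycles 6 and 7.** They are not. The cutoff in 5.9 applies only to those who do not resume. For those who do, the whole interval lies inside the window.
- **The 24-hour rule cannot be applied.** A site may simply report the event. The difficulty is that it may not yet know whether it must.
- **90% of visits or events are affected.** The 26 of 29 counts calendar days. The documents give no distribution of visit timing, and a four-week visit leaves no gap. Many patients may not get that far: median TTP/PFS was 1.6 months in the earlier PTCL cohort (Table 1), whereas the last Cycle 6 dose falls on study day 155.
- **SAP 8.2 closes AE collection.** It defines on-treatment time for exposure. The AE inclusion rule is in SAP 7.1.

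A 30-day window is also not an error in itself, and a later visit can still record events from days 0 to 30.

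The contradiction remains. No reading satisfies both 5.2 with Table 5 and 5.9 with 8.6 for a new AE or unrelated SAE after day +30 in a patient who stops at the End of Cycle 6 visit.

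**Conclusion.** The point holds in a limited form. For patients who reach the End of Cycle 6 visit, the protocol gives two incompatible end dates for AEs and all-causality SAEs. They are up to 26 days apart by that visit, plus any delay to EOT; for patients who stop earlier the difference is at most 7 days. The events at issue are new AEs, and SAEs judged unrelated, from day +31 to the visit. Their reportability turns on the section followed and on a resumption decision that may come after the 24-hour limit. The differing rule for early new antitumor therapy is a second, separate inconsistency.

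The sizes assume 4 and 8 weeks mean 28 and 56 days, counted from the last dose actually given in Cycle 6. The documents do not allow an estimate of how many patients or events are involved. The primary ORR analysis is unaffected. The correction should be made because safety capture would otherwise vary by site and by response.

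**What to change.** **Protocol.** Reconcile 5.2, Table 5, 5.9, 5.10, 8.2, 8.6.1 and 8.6.2 to one end date, and align the Synopsis and Schedule of Assessments with them. For patients who complete Cycle 6, collect all AEs and SAEs regardless of causality until the later of 30 days after the last dose and the End of Cycle 6 visit, or the EOT visit if the patient stops. Reporting then no longer depends on whether Cycle 7 starts. Keep the existing provision for related SAEs beyond that date. State one rule for patients who start new antitumor therapy within 30 days of the last dose, and use it in every section.

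**SAP.** Add the matching upper date bound for AE tables in Section 7.1, and show events after day +30 in a separate row so that the 30-day figures stay comparable. Leave the on-treatment definition in SAP 8.2 alone, because it serves the exposure calculations.

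**Cost.** Wording changes in both documents, and up to 26 more days of AE recording to the End of Cycle 6 visit (plus any delay to EOT) for patients who stop there, at visits already scheduled. The downside is that a few more late, unrelated events will be recorded.
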